# Medical and scientific judgment should be exercised in deciding whether expedited reporting is appropriate in situations where none of the outcomes listed above occurred. Important medical events that may not be immediately life-threatening or result in death or hospitalization but may jeopardize the patient or may require intervention to prevent one of the other outcomes listed in the definition above should also usually be considered serious. Examples of such events include allergic bronchospasm requiring intensive treatment in an emergency room or at home or convulsions that do not result in inpatient hospitalization, or the development of drug dependency or drug abuse. A new diagnosis of cancer during the course of a treatment should be considered as medically important.

Non-hematologic SAEs CTCAE Grade 3 and above, and all subsequent follow-up reports will be reported to the Stanford Cancer Center Data and Safety Monitoring Committee (DSMC) using the study specific CRF regardless of the event's relatedness to the investigation. Following review by the DSMC, events meeting the IRB definition of 'Unanticipated Problem' will be reported to the IRB using eProtocol within 10 working days of DSMC review, or within 5 working days for deaths or life-threatening experiences.

AEs that do not meet the requirement for expedited reporting will be reported to the IRB as part of the annual renewal of the protocol.

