#### **Phase I Study of CPX-351: CLTR0305-101**

In this initial phase I study, the primary goal was to establish the maximum tolerated dose (MTD) for CPX-351 for recommendations on dosing for further phase II studies.

Pharmacokinetic assessments of plasma samples were made at every dose level and patients were monitored for signs of antileukemic activity. An induction course with CPX-351 administered on days 1, 3, and 5 over 90 minute infusions was designed to mimic the 7 day drug exposure with conventional 7+3 treatment. Patients with relapsed/refractory AML, ALL, and high risk MDS were eligible for the study. There were 43 pts with AML, 3 pts with ALL, and 2 pts with MDS who were treated. The median age of patients was 62 with an age range of 23-81. The starting dose of CPX-351 was 3 units/m^2, and studied dose levels were 3 (1 patient), 6 (1 patient), 12 (2 patients), 24 (4 patients), 32 (4 patients), 43 (4 patients), 57 (3 patients), 76 (3 patients), 101 (6 patients), and 134 units/m^2 (6 patients). There were 34 patients who were studied in the dose escalation part of the study.

Dose limiting toxicities were observed at the 10th dose level of 134 u/m^2 (3 DLTs in 3 patients of 6), including congestive heart failure (CHF; 1 pt), hypertensive crises (1 pt) and persistent cytopenia past 56 days (1 patient; recovery occurred at day 112). The patient with the CHF episode had prior 369 mg/m^2 daunorubicin and a total of 556 mg/m^2 including CPX-351, and as a result, phase II studies have included a cap of 500 mg/m^2 on cumulative anthracycline dose after one induction course of CPX-351 and patients with significant pre-existing cardiac disease were excluded. Thus 101 units/m^2 was found to be the MTD. An additional 14 patients were subsequently added to the 101 units/m^2 cohort during the expansion phase of the study to obtain additional safety and potential efficacy data, for a total of 48 patients. Grade 3 and 4 Non-hematologic toxicities included mucositis (1 pt), vomiting (1 pt), skin rash (3 pts), CHF (2 pts), elevated bilirubin (1 pt), and elevated transaminases (2 pts). In terms of initial efficacy data, of the total 48 patients, there were

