## **7.3 Serious Adverse Event Reporting Instructions**

The investigator must complete the Serious Adverse Event Report Form in English, assess the relationship to study treatment and send the completed form by fax within 24 hours to Celator and to the local IRB Office. The original and the duplicate copies of the Serious Adverse Event Form, and the fax confirmation sheet must be kept with the case report forms.

Follow-up information is sent to Celator or its designee as well as the local IRB office via the original Serious Adverse Event Form, re-stating the date of the original report. Either a new Serious Adverse Event Form is sent (stating that this is a follow-up), or the original one resent (with the new information highlighted and a new date provided). The follow-up should describe whether the event has resolved or continues, if and how it was treated, whether the patient continued or discontinued study participation. The form and fax confirmation sheet must be retained.

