### **7.3.2 Report of Adverse Events to the Institutional Review Board**

The Sponsor-Investigator will report serious adverse events to the Stanford Institutional Review Board (IRB) per institutional policy.

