### **11.2 Data and Safety Monitoring Plan**

The Stanford Cancer Center Data and Safety Monitoring Committee (DSMC) will be the monitoring entity for this study. The DSMC will audit study-related activities to determine whether the study has been conducted in accordance with the protocol, local standard operating procedures, FDA regulations, and Good Clinical Practice (GCP). In addition, the DSMC will regularly review serious adverse events and protocol deviations associated with the research to ensure the protection of human subjects. Results of the DSMC audit will be communicated to the IRB and the appropriate regulatory authorities at the time of continuing review, or in an expedited fashion, as needed.

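### Sections 7.4.1 and 11.2 disagree on which SAEs the DSMC sees, fatal complications of myelosuppression are not clearly SAEs, and the IRB rules do not match across 7.3, 7.3.2 and 7.4.1

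*Combined protocol and SAP*

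**What the plan says.** **What the DSMC receives.** The closing paragraphs of section 7.4.1 state: "Non-hematologic SAEs CTCAE Grade 3 and above, and all subsequent follow-up reports will be reported to the Stanford Cancer Center" committee, regardless of relatedness. No time limit is given for sending them. Sections 7.3 to 7.3.4 direct reports to the drug supplier, the IRB and the FDA, but none names the DSMC as a recipient.

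**What the DSMC reviews.** Section 11.2 makes the DSMC the monitoring entity and says "the DSMC will regularly review serious adverse events and protocol deviations associated with the research". It sets no organ-system or grade limit and no review interval.

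**What counts as an SAE.** The starred notes in 7.4.1 take myelosuppression and its complications out of the SAE definition and record them as ordinary AEs. The examples are uncomplicated febrile neutropenia, infection, and bleeding of grades 1 to 3. The reason given is that these are common and expected in AML and MDS.

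**What the IRB receives.**
- Section 7.3: the investigator must "send the completed form by fax within 24 hours to Celator and to the local IRB Office".
- Section 7.3.2: the sponsor-investigator "will report serious adverse events to the Stanford Institutional Review Board (IRB) per institutional policy".
- Section 7.4.1: "Following review by the DSMC, events meeting the IRB definition of 'Unanticipated Problem' will be reported to the IRB using eProtocol", and the timing is "within 10 working days of DSMC review, or within 5 working days for deaths or life-threatening experiences". AEs that do not need expedited reporting go to the IRB at annual renewal.

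**The concern.** The protocol presents prolonged myelosuppression as the leading safety issue. Section 5.1.7 reports deeper and longer cytopenias than with 7+3 in Study 204, and sections 4.5.1 and 7.1 give this as a reason for the dose level chosen. In the phase I study one dose-limiting toxicity was "persistent cytopenia past 56 days (1 patient; recovery occurred at day 112"). Yet the one written feed to the monitoring committee leaves out hematologic SAEs, and the exemption may remove some of the worst consequences of low counts before that feed applies.

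This matters more because little else watches safety during the trial. The only interim rule (12.2) concerns response. Section 4.3 allows stopping for unacceptable toxicity but gives no threshold.

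The reporting of results is affected too. SAEs are a primary safety measure in 10.1. Whether a fatal infection in neutropenia counts toward that measure depends on how the exemption is read.

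**Working it through.** The plan has no figure to reproduce here. The check follows typical events through the written rules.

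| Event | SAE under 7.4.1? | Sent to DSMC under 7.4.1? | At IRB in 24 hours under 7.3? |
|---|---|---|---|
| Grade 3 or higher SAE plainly outside the blood system, for example cardiac | Yes | Yes, no deadline | Yes |
| Fatal or life-threatening marrow aplasia | Meets the outcome criteria, but myelosuppression is exempt: unclear | No, if classed as hematologic | Only if classed as an SAE |
| Fatal infection during neutropenia | Meets the outcome criteria, but infection is listed as exempt: unclear | Probably, if an SAE (step 2) | Only if classed as an SAE |
| Grade 4 or 5 bleeding with thrombocytopenia | Yes by implication, since only grades 1 to 3 are listed as exempt | Either way, term undefined | Yes |
| Long cytopenia with recovery, not life-threatening | No, exempt | No | No |

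**Step 1, DSMC scope.** Section 11.2 gives a review duty and 7.4.1 gives the feed. The feed is narrower than the duty, by organ system and by grade. A site that follows 7.4.1 exactly leaves the committee unable to do what 11.2 describes for hematologic SAEs.

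**Step 2, meaning of non-hematologic.** Section 7.4.1 does not define it. Section 6.1.1 lists febrile neutropenia and infection as exceptions to non-hematologic toxicity, which implies that they otherwise belong to that class. So an infection accepted as an SAE would probably reach the DSMC. Marrow aplasia would not. Nothing in the text settles bleeding.

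**Step 3, the exemption.** It sets a severity limit for bleeding (grades 1 to 3) and a qualifier for febrile neutropenia (uncomplicated). Infection carries no clear limit. A fatal or life-threatening case meets the first or second SAE criterion and also falls in the exempted class, and the text does not say which prevails. If the exemption prevails, the event misses the DSMC feed and the 24-hour rule, and reaches the IRB only at annual renewal.

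**Step 4, IRB rules.**
- 7.3: all SAEs, 24 hours, no start point stated.
- 7.3.2: SAEs, institutional policy, no time stated.
- 7.4.1: Unanticipated Problems only. The 10 working days run from a DSMC review that has no due date. The 5 working days for deaths or life-threatening events do not restate their start point.

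By contrast, 7.3.3 ties its 7-day and 15-day FDA limits to awareness of the event.

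**Step 5, scale, for illustration only.** The inputs are the CPX-351 arms of Studies 204 and 205 (sections 5.1.7 and 7.1) and the planned 33 patients. Expected count = 33 × rate.
- Deaths by Day 60: 33 × 4/85 = 1.6 (Study 204) and 33 × 0.148 = 4.9 (Study 205).
- Fatal bleeding, Study 204: 3/85 = 3.5%, and 33 × 3/85 = 1.2. The chance of at least one is 1 − (82/85)^33 = 0.69.
- Grade 3–4 febrile neutropenia, Study 204: 54/85 = 63.5%, and 33 × 54/85 = 21.

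These rates come from other populations, and section 4.5.1 says that the present dose is lower than in the earlier phase II studies. They show only that the unclear cases may well arise.

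**The case against.** The strongest reply has four parts.

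- **The exemption is a stated and reasonable choice.** If some 21 of 33 patients had febrile neutropenia, treating each case as an SAE would bury the useful signals. This stands for expected, uncomplicated events. It does not explain why fatal or life-threatening cases are left unaddressed. One could extend the word uncomplicated to infection as well, but the text does not require that.
- **Section 11.2 is not limited, so the DSMC may see everything.** This stands in part: the two sections conflict, and hematologic SAEs are not settled as excluded. But 11.2 creates no route by which events arrive.
- **The 7.4.1 report to the IRB may be additional.** It uses a different channel and covers Unanticipated Problems, so it can be read alongside the 24-hour report. This is plausible, but the protocol does not say so.
- **Section 7.3.2 may only point to the policy described in 7.4.1.** This is also possible. It states no time of its own, so it is better called unclear than contradictory.

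Three stronger readings are tempting and are not supported. A reader might infer that the DSMC is the body that must act on toxicity, but 11.2 gives it audit, review and communication duties, and 4.3 names no decision-maker. A reader might infer that a death could reach the IRB with no upper time limit, but 7.4.1 does not waive 7.3, so any death classed as an SAE is still due there within 24 hours. And a reader might take the Study 204 causes of early death (three bleeding, one pneumonia) or the phase I cytopenia as the share of harm that would go unreported. Those counts come from other trials and depend on classification. The phase I case is not described as life-threatening.

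**Conclusion.** The point holds as a conflict between stated rules and should be corrected. Three parts are established from the text:

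1. The DSMC feed in 7.4.1 is narrower than the review scope in 11.2, has no deadline, and rests on an undefined term.
2. The SAE exemption does not say whether fatal or life-threatening complications of myelosuppression remain SAEs. On one reading they miss both the DSMC and the 24-hour rule.
3. IRB reporting has differing scopes and clocks, some without a start point.

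The effect is on safety oversight and on the SAE tally. The sample size, the response rule, and the counts of 30-day and 60-day mortality are unaffected, since deaths are counted whatever their SAE class. The number of events that would be misdirected cannot be estimated from the documents. The conclusion assumes that staff apply 7.4.1 as written and that no institutional policy outside the documents fills the gap.

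**What to change.** Reconcile 7.3, 7.3.2, 7.4.1 and 11.2:

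- In 7.4.1, delete the non-hematologic limit so that hematologic SAEs reach the DSMC, and make the remaining grade limit agree with 11.2.
- State in 7.4.1 that the exemption for myelosuppression and its complications does not cover fatal or life-threatening events. Deleting the limit alone would not be enough, because exempted events never become SAEs.
- Send every death through Day 60, whatever its cause, to the DSMC within a stated time from site awareness. The 24 hours already used for the drug supplier is one option. Mortality to Day 60 is already a primary safety measure, so the data are collected.
- Give one IRB timeline with a stated start point, and say whether the eProtocol report is in addition to the 24-hour report.

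The cost is a wording amendment and some extra forms copied to the DSMC. At the illustrative rates above, Day 60 deaths would account for about 2 to 5 of these over the whole trial. Uncomplicated, expected events would stay exempt, and no new patient procedures are needed.

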## **8. CORRELATIVE/SPECIAL STUDIES**

**8.1 Laboratory Correlative Studies:** the following studies are completed for patients in the study as part of institutional routine care. We will evaluate molecular and cytogenetic data as available and compare to response.

**8.2 Collection of Correlative Studies:** Mutational and cytogenetic evaluation and bone marrow biopsy are routinely clinically obtained on initial evaluation at Stanford to confirm and evaluate current status of disease. These studies may be evaluated as clinically indicated at the time of relapse or progression of disease depending on diagnosis (AML or MDS). They will be collected as per standard institutional guidelines.

**8.3 Handling of Specimens:** Specimens are obtained as part of institutional routine care. They will be handled as per institutional standard guidelines.

**8.4 Specimen Shipping.** Mutational tests may be performed as a send out test by the institution. Specimens will be shipped per institutional guidelines by the institution lab.

**8.5 Specimen Coding.** Specimens are obtained as per routine care. Specimens will be coded as per institutional routine.

## **9. STUDY CALENDAR**

Please see Appendix for patient calendar.

## **10. MEASUREMENTS**

### **10.1 Primary and Secondary Outcome measures**

Primary outcome measures will be the following:

- Safety data. Safety data will be assessed using CTCAE v4.0:
  - 30 and 60 Day mortality
  - SAEs
  - Grade 3-5 AE frequency
- Determine the response rate (CR + CRi for AML + CR for MDS) following induction with CPX-351 **Secondary outcome measures will be the following:**
- Determine the duration of remission following induction with CPX-351.
- Determine overall survival at 12 months.
- Determine the early induction mortality at Day 60 after 1st induction.

#### **10.1.1 Relevant Subset**

- Safety data will be determined on all patients who have received at least one dose of CPX-351
- Response rate will be determined using all patients who have received at least one dose of CPX-351
- The duration of remission will be determined for all patients who achieve a CR or CRi.
- Overall Survival will be determined on all patients
- Early induction mortality will be determined on all patients who have received at least one dose of CPX-351

#### **10.1.2 Measurement Time Points**

- Safety data will be assessed for 4 weeks following completion or discontinuation of treatment, or until initiation of new therapy, whichever one comes first.
- The response rate will be determined following the initial course of therapy (e.g. up to two courses of induction therapy with CPX-351).
- Overall survival will be determined at 12 months
- Early induction mortality will be determined on Day 60 after 1st induction (Day 1=first dose of CPX-351)
- Remission duration is from the start of response until disease relapse or death. A response will be classified as CR or CRi for AML, and CR for MDS

#### **10.1.3 Response Review**

Responses are based on pathological responses. Pathology is routinely determined by hematopathologists at Stanford who are independent of the study at Stanford.

#### 10.1.4 Measurement Definitions

##### **Measurement definitions for patients:**

- Safety Data will be measured by CTCAE 4.0 criteria
- The response rate is the sum of the rate of CR plus CRi (Total of CR + CRi for AML patients + CR for MDS)
- For the following definitions involving blast percentages, blast percentages are routinely evaluated from bone marrow aspirate specimens by morphology. Evaluation of bone marrow biopsy is allowed for evaluation if the aspirate is insufficient for analysis, equivocal, dilute or aspicular.
- Responses for AML will use the European Leukemia Net (ELN) classification [21]
- Responses for MDS will use the International Working Group (IWG) guidelines [22]
- For treatment failure definitions as per the IWG criteria, we will consider up to two courses of induction therapy as the “initial course of therapy”

##### **Response Criteria for AML:**

- Morphologic leukemia-free state is defined as having < 5% blasts by morphology from the Day 14 bone marrow aspirate following induction therapy. Day 14 bone marrows may be obtained +/- 3 days due to logistic purposes of institutional bone marrow processing. There should be no blasts with auer rods or persistence of extramedullary disease.
- Complete remission (CR) is defined as having < 5% blasts, with count recovery to platelets  $\geq 100,000/\mu\text{L}$  and ANC  $> 1000/\mu\text{L}$ . There should be no blasts with auer rods and no persistence of extramedullary disease. Patient should have transfusion independence.
- Complete remission with incomplete count (CRi) recovery is defined meeting all the parameters for CR, with the exception of platelets  $\geq 100,000/\mu\text{L}$  and/or ANC  $> 1000/\mu\text{L}$ .
- Partial response is defined as normalization of blood counts (ANC  $> 1000/\mu\text{L}$  and platelets  $> 100,000/\mu\text{L}$ ); a decrease of bone marrow blast percentage to 5-25%; and decrease of pretreatment bone marrow blast percentage by at least 50%; or  $\leq 5\%$  blasts with auer rods still present.
- Resistant disease is defined as failure to achieve a CR/CRi following up to two courses of induction therapy with CPX-351. It only includes patients surviving  $\geq 7$  days following completion of initial treatment with evidence of persistent leukemia by blood or bone marrow aspiration
- Death in aplasia: deaths occurring  $\geq 7$  days following completion of initial treatment while cytopenic; with an aplastic or hypoplastic bone marrow obtained within 7 days of death, without evidence of persistent leukemia
- Death from indeterminate cause: deaths occurring before completion of therapy or  $< 7$  days following its completion; or deaths occurring  $\geq 7$  days following completion of initial therapy but no blasts in the blood, but no bone marrow examination available
- Disease relapse after CR/CRi: bone marrow blasts  $\geq 5\%$  (not attributable to any other causes such as regenerating bone marrow; if equivocal after recent therapy whether from marrow regeneration, a repeat bone marrow biopsy at least one week later should be done); reappearance of blasts in the blood; development of extramedullary disease
- Overall survival is defined as the number/percentage of patients alive at 12 months (starting from date of entry into trial). Includes death from any cause.

- Early induction mortality at Day 30 is defined as the number of patients who died during the first 30 days of treatment (with Day 1=first day of treatment) of the first induction
- Early induction mortality at Day 60 is defined as the number of patients who died during the first 60 days of treatment (with Day 1=first day of treatment) of the first induction
- Remission duration: is the number of days from remission until disease relapse (day when blasts > 5% are observed). It is defined for only patients who achieve a CR/CRi.
- Relapse free survival is defined for patients who achieve a CR/CRi in AML and is measured from the date of attaining remission until date of AML relapse or death from any cause.
- Event free survival is defined as time from date of entry into study until treatment failure, relapse from CR/CRi, or death from any cause (whichever occurs first). For patients who do not achieve a CR, EFS is defined as the point of progression or death (whichever comes first).

**Response Criteria for MDS: Responses must last for at least 4 weeks as per IWG criteria**

- Complete remission is defined as  $\leq 5\%$  blasts with normal maturation of all cell lines; persistent dysplasia will be noted; there must be normalization of peripheral blood counts to: Hb  $\geq 11$  g/dL, platelets  $\geq 100,000/\mu\text{L}$ , ANC  $\geq 1000/\mu\text{L}$  with no blasts in the peripheral blood.
- Partial remission is defined as meeting all CR criteria except: bone marrow blasts are decreased by  $\geq 50\%$  over pretreatment value but still  $> 5\%$
- Marrow CR is defined as having bone marrow  $\leq 5\%$  myeloblasts and decrease by  $\geq 50\%$  over pretreatment
- Stable disease is defined as failure to achieve at least PR, but no evidence of progression for  $> 8$  weeks
- Treatment failure is defined as:
  - death during treatment; or
  - disease progression characterized by worsening of cytopenias; or
  - increase in percentage of bone marrow blasts;
  - or progression to a more advanced MDS FAB subtype than pretreatment
- Relapse after CR or PR: at least one of the following:
  - Return to pretreatment bone marrow blast percentage
  - Decrement of  $\geq 50\%$  from maximum remission/response levels in granulocytes or platelets
  - Reduction in Hb concentration by  $\geq 1.5$  g/dL or transfusion dependence
- Disease progression. For patients with:
  - Less than 5% blasts:  $\geq 50\%$  increase in blasts to  $> 5\%$  blasts
  - 5-10% blasts:  $\geq 50\%$  increase in blasts to  $> 10\%$  blasts
  - 10-20% blasts:  $\geq 50\%$  increase in blasts to  $> 20\%$  blasts
  - 20-30% blasts:  $\geq 50\%$  increase in blasts to  $> 30\%$  blasts
  - Any of the following:
    - At least 50% decrement from maximum remission/response in granulocytes or platelets
    - Reduction in Hb  $\geq 2$  g/dL
    - Transfusion dependence
- Overall survival is defined as the number/percentage of patients alive at 12 months (starting from date of entry into trial). Includes death from any cause.

- Early induction mortality at Day 30 is defined as the number of patients who died during the first 30 days of treatment (with Day 1=first day of treatment) of the first induction
- Early induction mortality at Day 60 is defined as the number of patients who died during the first 60 days of treatment (with Day 1=first day of treatment) of the first induction
- Remission duration: is the number of days from CR until disease relapse.
- Event free survival is defined as time from date of entry into study until treatment failure or death from any cause (whichever occurs first).

